7.1.2. Drug Induced Vascular Inflammation and Complement Stopping Criteria

If any of the following are observed, results should be confirmed with a repeat sample collection and analysis, and if confirmed, further evaluation for alternative causes should be pursued in consultation with the Medical Monitor.

Repeat sample collection of C3, C4, Bb, C5a would be triggered by changes in the clinical signs and symptoms of complement activation ($\geq 2+$ haematuria; increasing urine ACR; vasculitic or purpuric rash; peripheral neuropathy; jaundice). Additional complement analyses for example CH50, Factor B level, Factor H level, sC5b-9 should also be considered in discussion with the Medical Monitor and Safety Panels.

1. **Persisting & deteriorating longitudinal trends in change from baseline for C3 and/or C4 defined as:**
 - a. If participant's baseline C3 and/or C4 is **within** the lab's normal range at baseline: there is a sequential decline in C3 and/or C4 once levels have fallen below the lower limit of normal (LLN) for ≥ 4 weeks OR
 - b. If participant's baseline C3 and/or C4 is **below** the lab's LLN at baseline: there is further sequential decline in C3 and/or C4 for ≥ 4 weeks OR
 - c. Regardless of baseline C3 and/or C4 level: there is a **$\geq 80\%$ reduction** in the participant's C3 and/or C4 level at any point
AND
 - d. There is an associated **≥ 3 -fold increase** in Bb and/or C5a from participant's baseline OR

- e. There are associated biochemical sequelae for example, a rising high sensitivity C-reactive protein (hs-CRP); rising monocyte chemoattractant protein (MCP-1); new thrombocytopenia, new renal impairment with no other explanation such as intercurrent infection OR
- f. There are associated clinical sequelae, for example, $\geq 2+$ haematuria; increasing urine ACR; vasculitic or purpuric rash; peripheral neuropathy; jaundice OR
- g. There is new cANCA or pANCA positivity

2. Persisting & deteriorating longitudinal trends in change from baseline for Bb and/or C5a where

- a. There is a ≥ 3 -fold increase in Bb and/or C5a over baseline AND
- b. This is persisting or increasing week on week in sequential data plots OR
- c. There are associated biochemical sequelae for example, a rising hs-CRP; rising MCP-1, new thrombocytopenia, new renal impairment with no other explanation such as intercurrent infection OR
- d. There are associated clinical sequelae, for example, $\geq 2+$ haematuria; increasing urine ACR, vasculitic or purpuric rash; peripheral neuropathy; jaundice or any combination of these OR
- e. There is new cANCA or pANCA positivity

Treatment Hold/Treatment Discontinuation

- Hold study treatment during evaluation of alternative causes for decreased C3 and/or C4 associated with increased inflammatory markers including one or more of hs-CRP, MCP-1, Bb and C5a
- Discontinue study treatment permanently if persistent change from baseline (≥ 4 weeks) in biomarker pattern (decreased C3/C4 associated with increased inflammatory markers including one or more of hs-CRP, MCP-1, Bb, C5a) without clear alternative explanation.
- Discontinue study treatment permanently if suspect clinical sequelae of complement activation, drug induced vascular inflammation, vasculitis or auto-immunity regardless of biomarkers changes or persistence.

7.1.3. Haematological Stopping Criteria

If a participant develops signs or symptoms of thrombocytopenia, obtain a platelet count (local lab) as soon as possible and hold dosing until the platelet count is confirmed.

If the platelet count is uninterpretable or a decreasing trend is noted below LLN reference range, re-check the platelet counts as soon as possible (the investigator may, at their discretion, opt to have the participant come to their next scheduled visit OR ask the participant to come earlier than their scheduled visit, as they feel appropriate based on review of the participant's clinical presentation and laboratory results). Samples showing platelet clumping should also be repeated.

Participants with platelet values below $75 \times 10^9/L$ will undergo further assessment including, but not necessarily limited to, anti-platelet antibodies. If the participant has a positive anti-platelet antibody, study treatment should be discontinued permanently. Monitor until platelet abnormalities resolve, stabilize, or return to within baseline values.

Table 8 Haematological Stopping Criteria

Platelet Count	Monitoring	Treatment
$75 \times 10^9/L \leq$ Platelets $<100 \times 10^9/L$	Monitor weekly, results of local platelet count must be available prior to dosing	Hold treatment until platelets return to $\geq 100 \times 10^9/L$ [if positive for anti-platelet antibodies, study treatment should be discontinued immediately]
$50 \times 10^9/L \leq$ Platelets $<75 \times 10^9/L$	Monitor every 2-3 days until three successive measurements $\geq 75 \times 10^9/L$, then weekly Assess anti-platelet antibodies	Discontinue treatment permanently Glucocorticoids recommended (unless the participant has a medical contraindication to receiving glucocorticoids), and discontinuation of any antiplatelet medicinal products/NSAIDs/anticoagulants
$<50 \times 10^9/L$	Monitor daily until $\geq 25 \times 10^9/L$, monitor every 2-3 days until three successive measurements $\geq 75 \times 10^9/L$, then weekly until platelets $\geq 100 \times 10^9/L$ Assess anti-platelet antibodies	Discontinue treatment permanently Glucocorticoids recommended (unless the participant has a medical contraindication to receiving glucocorticoids), and discontinuation of any antiplatelet medicinal products/NSAIDs/anticoagulants

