7.1.4. Drug Induced Kidney Injury (Renal) Stopping Criteria

Participant Level Stopping Criteria

- Hold study treatment in participants who develop ACR $\geq 0.5 \text{ mg/mg}$ (500 mg/g), or eGFR $>25\%$ reduction from baseline, pending consultation with the Medical Monitor and further evaluation of the cause.
 - If a dose is held, once eGFR increases to within baseline, ACR decreases to $<0.5 \text{ mg/mg}$ (500 mg/g), or the underlying cause of the decline in renal function is corrected, weekly dosing may be reinitiated after consultation with the Medical Monitor
- Hold study treatment in participants with ACR $\geq 2 \text{ mg/mg}$ (2000 mg/g), perform further evaluation for acute glomerulonephritis, as clinically indicated. If acute glomerulonephritis is confirmed or probable (i.e., meets clinical definition of rapidly progressive glomerulonephritis [RPGN] if biopsy not feasible), GSK3228836 should be permanently discontinued
- Delay in treatment of suspected RPGN should be avoided.

If any of the following are observed, results should be confirmed, and if confirmed, further evaluation for alternative causes should be pursued in consultation with the Medical Monitor:

- Persistent ACR ≥ 0.03 mg/mg (≥ 30 mg/g)
- Blood in urinalysis ≥ 5 RBC per high power field (HPF) confirmed by urine microscopy
- Persistent elevation of serum creatinine (>26.52 μ mol/L or 0.3 mg/dL change from baseline)

Following confirmation of the criteria above, further evaluation may include but not be limited to a 24-hour urine analysis, consultation with a nephrology specialist, renal ultrasound, urine microscopy, serum urea and creatinine, platelet count, urgent serum vasculitis screen [including ANCA, ANA, dsDNA, cryoglobulins], serum protein electrophoresis (SPEP)/urine protein electrophoresis (UPEP), and complement panel (C3, C4, C5a and Bb). Further evaluation and actions should be determined by the investigator in consultation with the Medical Monitor.

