- Participants approved by GSK for restart of study intervention must return to the clinic twice a week for liver function tests until stable liver function tests have been demonstrated and then standard laboratory monitoring may resume as per protocol.
- If the participant meets protocol-defined liver chemistry stopping criteria after study intervention restart, study intervention should be permanently discontinued.
- The Medical Monitor and the IRB/IEC must be informed of the outcome for the participant following study intervention restart.
- GSK must be notified of any adverse events.

For treatment that has been placed on hold, please follow the guidelines above (Section 7.1.1 to Section 7.1.4).

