8. STUDY ASSESSMENTS AND PROCEDURES

- Study procedures and their timing are summarized in the SoA (see Section [1.3](#)).
- In selected sites/countries, participants will have the option to use a centralised home nursing provider. Only selected visits will have the option to be performed as a home visit, these will include drug administration, blood draws, participant assessments and data collection. The full specifications of the home nursing services will be outlined in the SRM
- Protocol waivers or exemptions are not allowed
- Immediate safety concerns should be discussed with the sponsor immediately upon occurrence or awareness to determine if the participant should continue or discontinue study intervention.
- Adherence to the study design requirements, including those specified in the SoA, is essential and required for study conduct.
- All screening evaluations must be completed and reviewed to confirm that potential participants meet all eligibility criteria. The investigator will maintain a screening log to record details of all participants screened and to confirm eligibility or record reasons for screening failure, as applicable.
- Procedures conducted as part of the participant's routine clinical management (e.g., blood count) and obtained before signing of ICF may be utilized for

screening or baseline purposes provided the procedure met the protocol-specified criteria and was performed within the time frame defined in the SoA.

- Repeat or unscheduled samples may be taken for safety reasons or for technical issues with the samples.

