10.2. Appendix 2: Clinical Laboratory Tests

The tests detailed in [Table 11](#) will be performed by the central laboratory. Local laboratory samples may still be collected as needed by the site.

Local laboratory results are required for analysis of platelets during the dosing period and be available for the investigator's review prior to dosing. A sample for central analysis is obtained in parallel

Otherwise, local laboratory results are only required in the event that the central laboratory results are not available in time for either study intervention administration and/or response evaluation. If a local sample is required, it is important that the sample for central analysis is obtained in parallel.

Protocol-specific requirements for inclusion or exclusion of participants are detailed in Section [5](#) of the protocol.

Additional tests may be performed at any time during the study as determined necessary by the investigator or required by local regulations.

Pregnancy Testing:

Refer to Section [5.1](#) Inclusion Criteria for screening pregnancy criteria. Additional serum or urine pregnancy tests may be performed, as determined necessary by the investigator or required by local regulation, to establish the absence of pregnancy at any time during the participant's participation in the study.

Table 11 Protocol-Required Laboratory Tests

Laboratory Assessments	Parameters			
Hematology	Platelet Count ¹	RBC Indices: MCV MCH	WBC count (with Differential if WBC abnormal): Neutrophils Lymphocytes Monocytes Eosinophils Basophils	
	RBC Count			
	Hemoglobin			
	Hematocrit			
Clinical Chemistry	Blood Urea Nitrogen (BUN)	Potassium	Aspartate Aminotransferase (AST)/ Serum Glutamic-Oxaloacetic Transaminase (SGOT)	Total, indirect and direct bilirubin
	Creatinine	Sodium	Alanine Aminotransferase (ALT)/ Serum Glutamic-Pyruvic Transaminase (SGPT)	Total Protein

Laboratory Assessments	Parameters			
	Glucose	Calcium	Alkaline phosphatase	Albumin
Routine Urinalysis	
 • By dipstick • Microscopic examination (if blood or protein is abnormal) 			
Pregnancy testing	
 • Highly sensitive urine or serum human chorionic gonadotropin (hCG) pregnancy test (as needed for women of childbearing potential)² 			

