Other Tests	
 • Follicle-stimulating hormone and estradiol (as needed only) • Serology (HIV antibody, hepatitis C virus antibody, and hepatitis D virus antibody) • Hepatitis B serology (hepatitis B surface antigen [HBsAg], hepatitis B surface antibody [anti-HBsAg], hepatitis B e antibody [anti-HBeAg], Hepatitis B virus DNA [HBV DNA], Hepatitis B virus RNA [HBV RNA], Hepatitis B core related antigen [HBcrAg]) • Other laboratory: PT, INR, aPTT, Alpha-fetoprotein, ANCA (MPO-ANCA, PR3-ANCA), APRI/Fibrosure, Complement factors C3, C4, C5a, and Bb, hs-CRP, MCP-1, angiopoietin II, PBMC, soluble protein, PAX Gene • Urine ACR • Genetic sample • Viral Sequencing: HBV Genotype, HBV DNA, HBV RNA 
All study-required laboratory assessments will be performed by a central laboratory, with the exception:
 
 • Platelet counts for investigator decisions may be drawn at local laboratory 
 • PBMCs may be processed at the local laboratory as agreed with the Sponsor in advance. 			
Additional tests listed under safety follow-up processes	
Liver Chemistry Stopping Criteria³
 
 • Viral hepatitis serology including: 
 ○ Hepatitis A IgM antibody; ○ Cytomegalovirus IgM antibody; ○ Epstein-Barr viral capsid antigen IgM antibody (or if unavailable, obtain heterophile antibody or monospot testing); ○ Hepatitis E IgM antibody ○ Hepatitis B virus DNA load ○ Hepatitis C virus RNA load ○ Hepatitis D virus antibody • PK sample • Serum creatine phosphokinase (CPK) and lactate dehydrogenase (LDH). • Fractionated bilirubin, Anti-nuclear antibody, anti-smooth muscle antibody, Type 1 anti-liver kidney microsomal antibodies and quantitative total immunoglobulin G (IgG or gamma globulins). • Serum acetaminophen adduct high performance liquid chromatography (HPLC) assay 			

Laboratory Assessments	Parameters
	
Drug Induced Vascular Inflammation and Complement Stopping Criteria
 
 • CH50 • Factor B level • Factor H level • sC5b-9
	
Hematological Stopping Criteria
 
 • anti-platelet antibodies

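### Anti-platelet antibody testing has no explicit trigger in the 75 to <100 x10^9/L platelet band, the only band where a positive result changes treatment

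*Protocol*

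**What the plan says.** Protocol 7.1.3 sets three platelet bands in Table 8. In the two lower bands (50 to <75 and <50 x10^9/L) the monitoring column calls for an antibody assessment and the treatment column stops dosing permanently.

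The top band (75 to <100) is different. Its monitoring cell reads "Monitor weekly, results of local platelet count must be available prior to dosing". Its treatment cell holds dosing until platelets reach at least 100 x10^9/L, and a bracket adds "if positive for anti-platelet antibodies, study treatment should be discontinued immediately".

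The text before the table ties the work-up to the same lower threshold: participants below 75 "will undergo further assessment including, but not necessarily limited to, anti-platelet antibodies", and a positive result means permanent discontinuation.

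Other places that bear on this:

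- Section 7.1.5 on holds: "For treatment that has been placed on hold, please follow the guidelines above", meaning 7.1.1 to 7.1.4. It adds no release condition for a platelet hold.
- Appendix 2 (10.2), "Table 11 Protocol-Required Laboratory Tests", names anti-platelet antibodies under "Hematological Stopping Criteria", with no platelet band.
- The Schedule of Activities (1.3) has platelet counts but no antibody test.
- SAP 4.5.3.1 reports haematological monitoring and stopping events from platelet counts and anti-platelet antibodies.

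**The concern.** A test matters for dosing only if its result can change what is done. Below 75 it cannot, because everyone stops. At 75 to <100 it can, because a positive result turns a temporary hold into discontinuation. The written trigger covers the first case and leaves out the second.

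The stake is re-exposure. A participant whose count dips to, say, 85 and recovers to 100 meets the stated release condition with antibody status unknown. The protocol's own background makes this worth closing. Section 8.2.9.3 describes a rapid-onset, unpredictable thrombocytopenia that can end in fatal bleeding. Table 5 reports both recognised types in monkeys given this drug. Section 4.3 gives a plasma and tissue half-life of about 3 weeks, so a resumed dose cannot be withdrawn quickly.

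**Working it through.** **Step 1. Action under Table 8, by band and antibody status**

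| Platelets (x10^9/L) | Test explicitly triggered | Positive | Negative | Not tested |
|---|---|---|---|---|
| <50 | yes | stop | stop | stop |
| 50 to <75 | yes | stop | stop | stop |
| 75 to <100 | no | stop | hold, resume at >=100 | hold, resume at >=100 |

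The result changes the action only in the last row, the one without a trigger. A broken table in the PDF does not explain this, because the 7.1.3 text independently uses the <75 threshold. That text's instruction to stop on a positive result is also redundant below 75, where Table 8 already stops everyone.

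**Step 2. Is the test ordered elsewhere for this band?** The Schedule of Activities does not list it. Section 7.1.5 returns to the same criteria. Appendix 2 lets the investigator add tests at discretion. Table 11 names the test without a band. So testing is allowed and arguably implied, with no explicit trigger.

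**Step 3. Illustrative exposure.** The plan gives no figure to reproduce. Scheduled dosing days (Schedule of Activities) are 1, 4, 8, 11, 15, 22, 29, 36, 43, 50, 57, 64, 71 and 78: 14 x 300 mg = 4200 mg.

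Doses given with status unknown = number of dosing days on or after (day of low count + recovery time). Recovery times are assumed. Day 8 is the first scheduled haematology sample after dosing starts. Dosing is assumed to resume at 300 mg, with missed doses not made up.

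| Low count | 7-day recovery | 14-day | 28-day |
|---|---|---|---|
| Day 8 | 10 (3000 mg) | 9 (2700 mg) | 7 (2100 mg) |
| Day 29 | 7 (2100 mg) | 6 (1800 mg) | 4 (1200 mg) |
| Day 43 | 5 (1500 mg) | 4 (1200 mg) | 2 (600 mg) |
| Day 57 | 3 (900 mg) | 2 (600 mg) | 0 |

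For Day 8 with 7-day recovery, the doses are those on Days 15, 22, 29, 36, 43, 50, 57, 64, 71 and 78, which is 10.

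**Step 4. Frequency.** This needs the rates of entering the band, of antibody positivity, of recovery during dosing and of not being tested. The documents give none of them. Eligibility (5.2) excludes platelets below 140, so entering the band means a fall of more than 40/140 = 28.6% from any eligible screening value.

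**The case against.** The strongest reply is that the protocol already implies the test. Table 11 is headed as protocol-required, it names the antibody under the haematological stopping criteria, and section 8.2.5 says that required assessments defined in Appendix 2 must be carried out according to the laboratory manual and the Schedule of Activities. The laboratory manual is not among the documents reviewed. This stands in part: it rules out saying that nothing calls for the test. It does not supply a trigger, because Table 11 gives no band and the section that does give bands starts testing below 75.

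Second, Table 8 acts on a positive result, not on unknown status. A required work-up below 75 with discretionary testing above it is a conceivable tiered design. That is fair, but it would put the mandatory test exactly where it cannot alter dosing.

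Third, there are other safeguards: local platelet counts before dosing, a permanent stop below 75, regular review by the internal Safety Review Team, IDMC review about every 3 months, and the general rule "Immediate safety concerns should be discussed with the sponsor immediately upon occurrence or awareness". These limit harm, but none orders the antibody test.

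Fourth, one might contrast this hold with the renal hold, where "weekly dosing may be reinitiated after consultation with the Medical Monitor". Section 7.1.3 is indeed the only one of 7.1.1 to 7.1.4 that never mentions the Medical Monitor. The contrast should not be pressed, though. Liver holds in Table 7 also release to 150 mg weekly on a laboratory value, with Medical Monitor agreement specified for the return to 300 mg.

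**Conclusion.** The gap is real and limited. Section 7.1.3 explicitly triggers the antibody test only where the result cannot change dosing, and not in the 75 to <100 band, where it can. The stated release from the hold is a platelet count alone. The protocol's own stop rule therefore cannot be relied on in that band. It is worth correcting as a safety clarification, and it does not affect the primary estimand, which follows treatment policy for interruptions.

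Two stronger readings are tempting and not supported. A reader might infer that the protocol nowhere requires the test; Table 11 makes that too strong. A reader might also infer that dosing may resume only after a negative result; the bracket conditions on a positive one, and the documents do not say how well antibody status predicts later thrombocytopenia.

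On size, 0 to 10 of 14 doses (0 to 3000 mg) per affected participant is an illustration under assumed recovery times. It does not measure how often harm would occur. Table 5 reports no thrombocytopenia in the two earlier clinical studies, but dosing there lasted four weeks against 12 here.

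**What to change.** Add an instruction to assess anti-platelet antibodies to the monitoring cell of the 75 to <100 row in Table 8, and change the trigger in the 7.1.3 text from <75 to <100 x10^9/L. Draw the sample with the first repeat or weekly platelet count in the band, so that the assay runs while platelets recover.

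It is advisable to review the result before dosing resumes. Whether to make a negative result a formal condition is for the sponsor to decide, since assay turnaround is not stated either. Optionally, the SAP listing of haematological events could flag untested cases in this band as antibody not done.

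The direct cost is one extra blood test per participant entering the band, using a test already in Table 11. If resumption waits for the result, the hold may lengthen. After the loading period, each extra week costs one dose (1/14 = 7.1%). From Day 29, a 14-day hold gives 12/14 = 85.7% dose compliance and a 21-day hold gives 11/14 = 78.6%, which falls in the SAP's <80% descriptive category (6.1.5). During loading the cost is higher: a hold from Day 8 to Day 15 misses two doses, on Days 8 and 11.

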7.1.4. Drug Induced Kidney Injury (Renal) Stopping Criteria

Participant Level Stopping Criteria

- Hold study treatment in participants who develop ACR $\geq 0.5 \text{ mg/mg}$ (500 mg/g), or eGFR $>25\%$ reduction from baseline, pending consultation with the Medical Monitor and further evaluation of the cause.
 - If a dose is held, once eGFR increases to within baseline, ACR decreases to $<0.5 \text{ mg/mg}$ (500 mg/g), or the underlying cause of the decline in renal function is corrected, weekly dosing may be reinitiated after consultation with the Medical Monitor
- Hold study treatment in participants with ACR $\geq 2 \text{ mg/mg}$ (2000 mg/g), perform further evaluation for acute glomerulonephritis, as clinically indicated. If acute glomerulonephritis is confirmed or probable (i.e., meets clinical definition of rapidly progressive glomerulonephritis [RPGN] if biopsy not feasible), GSK3228836 should be permanently discontinued
- Delay in treatment of suspected RPGN should be avoided.

If any of the following are observed, results should be confirmed, and if confirmed, further evaluation for alternative causes should be pursued in consultation with the Medical Monitor:

- Persistent ACR ≥ 0.03 mg/mg (≥ 30 mg/g)
- Blood in urinalysis ≥ 5 RBC per high power field (HPF) confirmed by urine microscopy
- Persistent elevation of serum creatinine (>26.52 μ mol/L or 0.3 mg/dL change from baseline)

Following confirmation of the criteria above, further evaluation may include but not be limited to a 24-hour urine analysis, consultation with a nephrology specialist, renal ultrasound, urine microscopy, serum urea and creatinine, platelet count, urgent serum vasculitis screen [including ANCA, ANA, dsDNA, cryoglobulins], serum protein electrophoresis (SPEP)/urine protein electrophoresis (UPEP), and complement panel (C3, C4, C5a and Bb). Further evaluation and actions should be determined by the investigator in consultation with the Medical Monitor.

